Responsibilities: Preparation of ethics application and trial governance documentation, maintenance of trial documentation and master database, reporting of all adverse events, serious adverse events and suspected unexpected serious adverse reactions to the Ethics Committee (in accordance with HREC requirements), screening of participants, baseline assessment of participants, study dietitian and interventionist, data analysis and interpretation, preparation of manuscripts.

2. Resources

Resources necessary for the project to be conducted

The University of Sydney, Faculty of Health Sciences Cumberland Campus has the following resources which will be used during the study:

- Keiser pneumatic resistance training machines
- Treadmill
- Dual energy x-ray absorptiometry (DXA) scanner (Lunar Prodigy, GE Medical Systems, Madison, WI)
- Consumables for blood collection and storage
- Consumables for stool collection and storage
- -80 degree freezer
- Respiratory gas analysis system (Medgraphics PFX Ultima, USA),
- Axivity AX3 accelerometer
- 12-lead electrocardiogram

With considerations to the high risk of osteoporosis in individuals living with IBD including those with UC, the use of the DXA to assess bone mineral density as part of this project is of great importance and is usually included in standard of care. Identifying clinical features of participants with UC would further inform us of any potential risk associated with strength assessment and physical testing procedures. With consideration to apparently healthy participants without UC, assessment of bone mineral density would also allow us to identify any underlying issues and potential risks associated with strength assessment and physical testing procedures. It should be noted that the use of the DXA for this study has received Radiation Safety Approval as of 15/01/2019; approval number RSC1901.

2. SYNOPSIS

Ulcerative Colitis (UC) is a progressive, chronic condition defined by acute bouts of inflammation accompanied by severe gastrointestinal symptoms and periods of remission. Prevalence is increasing globally while mechanisms of the disease are poorly understood. Environmental factors including diet have been proposed as a determinant for UC aetiology; however evidence beyond epidemiological studies and animal studies has been limited. Particularly, the role of specific dietary elements and lifestyle interventions with the potential of facilitating clinical remission and improve symptoms has not been well characterised. Despite this gap in research, diet has been consistently identified to be a significant factor influencing disease progression and symptoms in those with UC. This highlights the need of robustly designed trials investigating the impact of dietary components and disease expression of UC in the active phase of the disease.

Separate lines of research have identified the Mediterranean Diet (Med Diet) as a dietary pattern of interest with consideration to inflammatory processes. The protective effects of the diet have been partially attributed to the use of olive oil as a primary fat source, and preliminary evidence has demonstrated its protective effects in experimental UC models. Dietary intake of olive oil appears to attenuate disease aetiology in animal models of colitis and modulate the gut microbiome, which has been hypothesised to influence mucosal healing and symptomatic improvements. Translation of these studies into human trials

however have been limited, with the majority of trials identified being uncontrolled clinical trials and retrospective studies. As such we will conduct a novel study examining the effects of chronic consumption of extra virgin olive oil on the gut biota and symptoms of community dwelling UC cohorts in comparisons to healthy controls. Secondary outcomes include markers of inflammation, macro and micronutrient intake, nutrition status and quality of life.

We hypothesise that replacement of usual dietary fats with extra virgin olive oil will improve disease activity scores in those with Ulcerative Colitis relative to the usual care control group. Additionally, the impact of extra virgin olive oil consumption will be distinct between those with active UC and healthy controls. Using results from past diet studies in UC, the effect size of diet was estimated to be 0.917. Sample size was calculated at an alpha of 0.05 and beta 0.8, resulting in an estimated sample size of 60 participants.

The COLONIC will be a novel study identifying the impact of dietary fat types on the disease expression of UC and changes to the gut microbiota in comparisons to healthy subjects without IBD.

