6.2 STUDY DESIGN

Participants will be divided into two groups; individuals with Ulcerative Colitis (n: 30) and healthy controls (n: 30). Participants within these two groups will be randomised after screening in a 1:1 ratio to nutrition intervention or usual care. We will use a concealed, computer-generated sequence of randomly permuted variable blocks of four or 6, stratified for presence/absence of disease and sex, generated by an online program created by a statistician not otherwise involved in the study, available at www.randomization.com. Randomisation will occur at the completion of the baseline assessment and will be concealed by a statistician not otherwise involved in the study. The baseline assessor will confirm the participant's assignment at the end of the study with this staff member and communicate the study allocation to the participant to discuss next steps.

Intervention arms

Treatment Group: Replacing free fats with extra virgin olive oil

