6.4 SAMPLE SIZE

Power Calculations:

At the time of writing, there were limited published papers identifying the effects of diet on active Ulcerative Colitis. We identified three studies on dietary intervention; 1 randomized controlled trial of a single food component (22) and two uncontrolled trials of a comprehensive diet intervention (23, 24). Only the two uncontrolled studies had enough information to allow for the calculation of an effect size. Hedges' bias corrected effect sizes were calculated from published means and standard deviations of a single group, pre-post study involving a dietary intervention over 8 weeks (23) and 6 weeks (24) (Table 1).

The effect size of a dietary intervention in active Ulcerative Colitis calculated from these studies were 0.917 (23) and 2.638 (24) respectively. With consideration to the current study design which includes adult populations and the use of the same scoring tool, we have selected the paper by Konijeti, et. al (24) to estimate sample size.

Table 1

Citation	Outcome	Baseline	Post dietary intervention	Mean difference	Pooled SD	Effect size	Sample size (n total)
Suskind et al., (23)	Pediatric Ulcerative Colitis Activity Index	28.3 (8.8)	6.7 (2.9)	- 21.6	6.6	0.917634	48
Konijeti et al., (24)	Partial Mayo Score	5.8 (1.2)	1.2 (2.0)	- 4.6	1.6	2.638281	16

The Partial Mayo Score is a validated 9-point, non-invasive method of assessing disease severity in Ulcerative Colitis comprising of stool frequency, bleeding, and subjective assessments of disease activity. Remission is set at ≤ 1 , Mild Disease between 2-4, Moderate Disease between 5-6, and Severe Disease ≥ 7 (25).

Based on the available evidence, we hypothesize that EVOO consumption would elicit a similar reduction to average Mayo Score in the intervention group compared to those randomized into the usual care group. Due to the single dietary intervention used in this study and accounting for the uncontrolled study cited, a conservative approach to estimate effect size was implemented.

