We calculated effect size based on a 2 point (22%) reduction in the Partial Mayo Score (less than half of the mean difference cited in literature), with alpha 0.05 and beta 0.8. Effect size was calculated to be 1.25, with a sample size of 12 participants per group (24 individuals with Ulcerative Colitis randomized to either the intervention or usual care) required to determine changes in disease activity post intervention. Accounting for a 16% dropout rate which occurred in both studies selected, we will aim to recruit 28 participants with Ulcerative Colitis.

With consideration to those without a history of Inflammatory Bowel Disease, we will also aim to recruit an equal number of participants. Due to the limited evidence available on the effects of EVOO consumption on the gut microbiome and inflammatory markers in apparently healthy individuals, the recruitment number of apparently healthy controls are not based on any hypotheses on the differences between those living with UC and non-IBD cohorts subjected to EVOO consumption or dietary intervention. In total, we will aim to recruit 56 participants for this study; 28 individuals with UC and 28 individuals without a history of IBD.

Expected duration of the study and start times

It is expected that the study will take four years to complete. This includes 6 months to set up the study, including recruitment and training of the study personnel, procuring study resources, and preparation of the recruitment and study materials.

It is expected that recruitment will begin no later than April 2019. We are aiming for a conservative estimate of 1 participant per week, and means all participants will be recruited by June 2020, however additional time has been allocated to account for delays related to other investigations, work and travel arrangements, and recent changes to therapy.

The baseline assessments will start in April 2019 and end latest by August 2020.

The post-intervention assessments will start in May 2019 and end by November 2020, with additional time allocated to account for unexpected delays in recruitment and assessment.

The main outcome publication will be prepared by early to mid-2021. Table 2 illustrates the overall project schedule.

Table 2. Colonic Project Schedule

	2018	2019				2020				2021
	Oct-Dec	Jan-Mar	Apr-Jun	Jul-Sep	Oct-Dec	Jan-Mar	Apr-Jun	Jul-Sep	Oct-Dec	Jan-Mar
Study protocol and ethics approval	X	X								
Set-up of the study	X	X								

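### The protocol gives two incompatible sample-size bases (0.917 with 60 in the synopsis, 1.25 with 56 in section 6.4), and 0.917 does not follow from its own row of Table 1

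*Protocol*

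**What the plan says.** Three places in the protocol fix the size of the trial.

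- **Section 2, Synopsis.** "Using results from past diet studies in UC, the effect size of diet was estimated to be 0.917". The next sentence reads: "Sample size was calculated at an alpha of 0.05 and beta 0.8, resulting in an estimated sample size of 60 participants".
- **Section 6.2, Study design.** The two populations are "individuals with Ulcerative Colitis (n: 30) and healthy controls (n: 30"), each randomised 1:1, which is 15 per arm within UC and 60 overall.
- **Section 6.4, Sample size.** Table 1 lists two uncontrolled pre-post studies, whose effect sizes, "calculated from these studies were 0.917 (23) and 2.638 (24) respectively", belong to a paediatric index and to the Partial Mayo Score in that order. The section selects the adult Partial Mayo study and cuts its effect to 2 points. It then states: "Effect size was calculated to be 1.25, with a sample size of 12 participants per group". Next comes dropout: "Accounting for a 16% dropout rate which occurred in both studies selected, we will aim to recruit 28 participants with Ulcerative Colitis". An equal number of healthy participants is added, and the section says that their number rests on no hypothesis. It concludes: "In total, we will aim to recruit 56 participants for this study".

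**The concern.** The effect size and total in the synopsis are not those of the section that derives the sample size. The 0.917 belongs to the study that section 6.4 considered and did not use. The recruitment target is 60 in two places and 56 in a third. In Table 1, the 0.917 stands beside a mean difference of 21.6 and a pooled SD of 6.6, whose ratio is above 3.

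An ethics committee or reader who relies on the synopsis would take away an effect size, a total and a power that cannot all be true together. The effect size also misreports the evidence as tabulated.

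**Working it through.** **Inputs.** Synopsis: effect size 0.917, alpha 0.05, total 60. Section 6.2: 15 UC per arm. Section 6.4: 2 points, pooled SD 1.6, 16% dropout. Table 1: paediatric row 28.3 (8.8) to 6.7 (2.9), n 48; adult row 5.8 (1.2) to 1.2 (2.0), n 16. The stated beta of 0.8 is read as power 0.8. Sidedness is not stated; two-sided is assumed unless noted.

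**1. Section 6.4 core figure.** d = 2/1.6 = 1.25. A two-sided two-sample t-test at 80% power needs 11.09, so 12 per arm, with 83% power. This reproduces the plan. A one-sided test would need 8.68, so 9 per arm; two-sided is therefore the likely intention.

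**2. Synopsis figure.** d = 0.917.
- Normal approximation, n = 2(1.96 + 0.84)²/0.917²: 19 per arm.
- Two-sided t-test: 19.68, so 20 per arm. That is 40 UC completers, and 40/0.84 = 47.6, so 48 UC recruits.
- One-sided t-test: 15.43, so 16 per arm (32).
- Four-group ANOVA with f = 0.917/2 = 0.4585: 56 in total.
- None of these is 60. A value near 60 appears only at 90% power with dropout (25 per arm by normal approximation; 50/0.84 = 59.5). That is not the stated power, and all 60 would have to have UC.

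Section 7.1 restricts the Partial Mayo assessment to participants with UC, so healthy participants add nothing to that comparison. Two-sided t-test power:

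| UC per arm | d = 0.917 | d = 1.25 |
|---|---|---|
| 12 | 57% | 83% |
| 14 | 65% | 89% |
| 15 | 68% | 91% |

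**3. Table 1.** Pooled SD = √((s₁² + s₂²)/2); g = (difference/SD) × (1 − 3/(4df − 1)), with df = n − 2.
- Adult row: SD = √((1.2² + 2.0²)/2) = 1.649; 4.6/1.649 = 2.789; × (1 − 3/55) = 2.637. The stated value is 2.638, so the method is identified.
- Paediatric row: SD = √((8.8² + 2.9²)/2) = 6.552; 21.6/6.552 = 3.297; × (1 − 3/183) = 3.243. The stated value is 0.917634.
- Other choices of df, and the rounded SD of 6.6, give 3.16 to 3.27. Varying n does not rescue 0.917: the corrected value is 0 at n = 3, 1.88 at n = 4 and rises from there.
- A value of 0.917634 would need an SD of 21.6/0.917634 = 23.5, against the tabulated 6.6. The stated and recomputed values differ by a factor of 3.24/0.917 = 3.5.

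**4. Dropout (minor).** 24 × 1.16 = 27.8, which gives the plan's 28. Keeping 24 after 16% loss needs 24/0.84 = 28.6, so 29, or 30 for equal arms. With 28, 28 × 0.84 = 23.5 remain. With 11 and 12 completers, power at 1.25 is still 81%. With 30, 30 × 0.84 = 25.2 remain.

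**5. Label (minor).** The 12 per arm follows from power 0.8, which is beta 0.2. The synopsis and section 6.4 both give beta as 0.8.

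**The case against.** The strongest reply is that section 6.4 is the operative calculation and that it is sound. It sets the paediatric study aside, so the 0.917 feeds no step of it, and 1.25 does lead to 12 per arm. This stands, and it limits the point to an unreconciled synopsis, two different targets and a wrong entry in an unused row.

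A reader might infer from the 68% that the trial is underpowered. The protocol does not support that. The 68% assumes a true effect of 0.917, which the protocol's own table contradicts; at 1.25, 15 per arm give 91%. The 68% shows only that the synopsis sentence does not hold together. It also takes the 30/30 split from section 6.2, since the synopsis does not say how its 60 divides.

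A reader might also infer that 3.24 is the correct published effect. That depends on the tabulated means and SDs having been copied correctly, and the cited study is not at hand. The row is inconsistent, but which entry is wrong cannot be settled from the protocol.

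Finally, the dropout slip costs one participant (two for equal arms) and does not take power below 80% at 1.25. It carries no weight on its own.

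**Conclusion.** The contradiction is real and should be corrected. The protocol attaches two effect sizes (0.917 and 1.25) and two totals (60 and 56) to one trial. The synopsis combination fails on its own terms: 20 UC per arm are needed and 15 are planned. The 0.917 is inconsistent with its row by a factor of about 3.5.

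The practical size is modest. The targets differ by 2 UC and 2 healthy participants, and both 28 and 30 UC keep at least 80% power for the 2-point difference after 16% dropout. These figures assume a two-sided t-test at alpha 0.05, an SD of 1.6 and power 0.80. The conclusion is that the stated justification is wrong, not that the planned number is too small.

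**What to change.** - **Synopsis:** replace the effect-size sentence with the section 6.4 basis: 2 points, SD 1.6, d = 1.25, alpha 0.05, power 0.80 (beta 0.20), 12 UC completers per arm. Say that the healthy group matches the UC number and is not powered.
- **Sidedness:** state it in section 6.4. Two-sided reproduces 12 per arm; the sponsor should confirm that this was meant.
- **Table 1 and its text:** recheck the paediatric row against its source and make it consistent. The effect size is about 3.24 if the tabulated means and SDs are right.
- **Dropout:** write 24/0.84 = 28.6, rounded to 30 UC for equal arms of 15.
- **Total:** use 30 UC + 30 healthy = 60 in the synopsis, section 6.2 and section 6.4.
- **Label:** in section 6.4 also, change beta 0.8 to power 0.80 (beta 0.20).

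The cost is wording, plus one check of a cited paper. The target stays as section 6.2 already has it, four participants above section 6.4 (60 − 56).

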3. RATIONALE / BACKGROUND

Ulcerative Colitis (UC) is an inflammatory bowel disease (IBD) mainly affecting the superficial mucosa of the large intestine (colon) and rectum. It is a chronic, progressive condition characterised by periods of acute inflammation and remission (1, 2). Typically associated with developed countries such as North America and Northern Europe, UC is emerging as a global disease. Prevalence has increased in recent years and developing nations, where the condition is uncommon, are reporting higher incidences in line with industrialization (3, 4). Interestingly several studies on UC prevalence in second generation migrants found comparable rates with the native population of the country they migrated to (5-7). This suggests that environmental factors significantly contribute to UC aetiology, and may hold clues for future adjunctive non-pharmacological approaches (8).

Diet as a modifiable risk factor in the development (2, 9) and progression (10, 11) of UC has been documented however poorly understood. Particularly, elements of the diet which promotes mucosal healing and facilitates remission in active disease remains uncertain, with a high degree of variability across studies (12). Consequently, evidence based dietary guidelines for the management of UC is severely lacking (13).

Separate lines of research have identified the protective role of a Mediterranean Diet (Med Diet) in inflammation (14) including in IBD (15). Part of this protective property may be attributed to the consumption of olive oil, contributing to a higher proportion of Oleic Acid (OA) in the diet (16, 17). Olive oil has demonstrable effects in animal models of colitis (18, 19) and effectively modulates the gut microbiota (20, 21), however well-designed human studies are limited.

As such, we will examine the effects of olive oil on the disease activity of UC and identify potential changes to the gut microbiome in human cohorts. We hypothesise that chronic olive oil consumption has marked effects on UC symptoms, gut microbiome profile, and inflammatory

markers. Additionally, we also hypothesise that the changes in the gut microbiome in those with UC will be distinct from the changes observed in healthy subjects without IBD.

4. AIMS

1. To conduct the first RCT of the effects of chronic extra virgin olive oil consumption on the human gut microbiota in both healthy and diseased states
2. To conduct the first RCT of the impact of extra virgin olive oil on the expression of UC in those with mild-moderate disease states
3. To assess the relationship between inflammation, gut microbiota changes and UC symptoms in response to a short term dietary prescription
4. To investigate the course of the alteration and persistence of the responses to dietary change by characterizing the gut microbiota and biological markers of the disease during the intervention period and any sustained or residual effects 4-weeks post-intervention.

Primary Hypotheses

1. Replacement of dietary fats with extra virgin olive oil will positively influence disease activity scores and disease symptoms
2. Dietary fat replacement will modulate the gut microbiota profile of those with UC and healthy controls.
3. Distinct changes in the gut biota will occur between participants with UC and healthy controls once exposed to the diet intervention, indicating the importance of gut microbiota in modulating disease outcomes.
4. The impact of short term dietary changes has longer term effects post cessation of the diet.

Secondary aims of the study will be to determine the effect of extra virgin olive oil on inflammatory markers of UC and quality of life measures, and characterization of dietary strategies in individuals living with UC. Adherence to the intervention protocol, weekly health status and adverse events also constitute secondary study outcomes.

6. RESEARCH PLAN / STUDY DESIGN

6.1 TYPE OF STUDY

A randomized, controlled, parallel clinical trial.

6.2 STUDY DESIGN

Participants will be divided into two groups; individuals with Ulcerative Colitis (n: 30) and healthy controls (n: 30). Participants within these two groups will be randomised after screening in a 1:1 ratio to nutrition intervention or usual care. We will use a concealed, computer-generated sequence of randomly permuted variable blocks of four or 6, stratified for presence/absence of disease and sex, generated by an online program created by a statistician not otherwise involved in the study, available at www.randomization.com. Randomisation will occur at the completion of the baseline assessment and will be concealed by a statistician not otherwise involved in the study. The baseline assessor will confirm the participant's assignment at the end of the study with this staff member and communicate the study allocation to the participant to discuss next steps.

Intervention arms

Treatment Group: Replacing free fats with extra virgin olive oil

The treatment groups for both participants with UC and healthy controls will be instructed to modify their current dietary intake by replacing a portion of their fat intake with extra virgin olive oil (EVOO) over a 4-weeks. We will aim to replace all free fats or fats added into meal preparation which includes but is not limited to cooking oil, fat spreads, butter, and oil based dips and sauces. For the purposes of this study, we will aim to ensure that energy intake between participant's usual diet and the intervention remains the same. As such, average energy contributions of free fats in the diet will be calculated, which will then be converted to the quantity of EVOO required to be consumed daily. Kitchen weight scales and marked bottles will be used to assist estimating the participant's daily requirement. The study dietitian will provide information on strategies to incorporate the oil into the participant's daily meals and a checklist for daily intake to assist with the behaviour change. If the participant is fasting for any reason during the study, the intervention will resume once the participant is able to consume meals again. No top ups from previous days will be required. For participants with shared meal preparation responsibilities in the household, additional bottles of EVOO will be provided. The EVOO used for this study will be Australian produced EVOO currently available for sale as a food item in accordance with Australian food regulations and will not be a special product or formulation. Upon completion of the 4 weeks of the intervention, all remaining EVOO bottles will be collected and participants will be requested to return to consuming their regular diet. During this 4-week washout period, participants will resume their usual intake of free fats to identify any sustained effects of the intervention.

Both during active intervention and the washout period, participants will be requested to maintain all their daily activities including physical activity, sleep and exercise. All of the documentation of changes in health care, habitual exercise or diet noted for the control group below will also be recorded in the intervention group.

Control Group: Usual Care

Participants will continue to receive usual care as documented at baseline. Any new medical therapy for UC commenced during the study period will be recorded, as well any change in chronic treatments for UC, surgeries, other new medical conditions or treatments, or other interventions employed for their known or purported health benefits (e.g., pre- and pro-biotic supplementation, acupuncture, hypnotherapy, and counseling). Participants will be asked to maintain their habitual lifestyle regarding diet and exercise throughout the study, but any changes they do make will be recorded.

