6.3 PARTICIPANTS & DATA COLLECTION

We will recruit men and women aged ≥ 18 years with Ulcerative Colitis who are able to provide written informed consent will be recruited from gastroenterologists as well as via community/social media advertising in the greater Sydney area.

Participants with UC Inclusion Criteria:

1. Aged ≥ 18 in 2018
2. Ulcerative colitis (UC) >3 months' duration of any extent.
3. Stable medication. No changes to medication or therapies in the preceding 4 weeks.

Participants with UC Exclusion Criteria:

1. Prior or concomitant fecal microbiota transplantation or any rectal preparations currently.
2. Antibiotic/anti-tuberculosis treatment for any reason during the study period or in the preceding 4 weeks.
3. Probiotic supplements or biological/monoclonal antibody agents during the study period or in the preceding 12 weeks. Food based probiotics such as yoghurt and kefir will be allowed.
4. Significant prior gastrointestinal surgery (e.g., colon resection, colectomy, appendectomy) or clinical evidence of any comorbid chronic disease that may interfere with the patient's ability to enter the trial and undertake the intervention planned.
5. Coexistent serious autoimmune disease such as rheumatoid arthritis or systemic sclerosis.
6. Planned major surgery within the first 3 months after randomization.
7. Pregnancy or female planning pregnancy within the first 3 months after randomization.
8. Participation in another clinical trial for with concurrent participation is deemed inappropriate.
9. Daily consumption of olive based product(s) in any form (including oil, pickles, tapenade, spreads, and supplements) as determined by the diet history and medication list

10. Currently on a special diet in which participation is deemed inappropriate (e.g. low residue diet, liquid diet, low fat diet)

We will also recruit men and women aged ≥ 18 years with no significant chronic or acute disease who are able to provide written informed consent to participate in the study as the healthy control group. Recruitment will be achieved through community/social media advertising in the greater Sydney area alongside the recruitment strategy for participants with UC.

Healthy Control Inclusion Criteria:

1. Aged ≥ 18 years in 2018
2. Willing to be randomized into one of the two study arms and participate in the intervention prescribed

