7.3 CONFIDENTIALITY AND PRIVACY

Data will be collected over the phone (telephone screening) and in person (assessments), using researcher-administered questionnaires, and physical testing. Data gathered from the screening process, assessment, and training sessions will be entered by the research staff into a database created in REDCap. Data will be entered in a re-identifiable form using unique identity numbers. This code will be used on all electronic data forms, electronic databases and hard copy data forms. No forms will contain the names of participants, or other identifying information.

All participant information will remain re-identifiable, so that information that is relevant to their medical care can be communicated to appropriate medical professionals. Participants will only remain re-identifiable to persons directly involved with the study, namely the Primary and Associate Investigators or HDR students who are conducting the intervention/ assessments. All data will be de-identified prior to depositing in a repository at the end of the study, as required by the National Health and Medical Research Council.

During screening, participants will be assigned a Screening ID. Participants who are found eligible for the study and consent to participate will be randomised by an investigator who is otherwise not involved in the study. Participants will then be issued with a Study ID Code. The Screening ID Code and Study ID code will be recorded in the randomisation database.

The investigator performing the randomisation will only be provided with Screening ID, age, and gender of the participant to perform the randomisation procedure. Once randomised, participant ID codes will not be removed, even if they choose to withdraw from the study.

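### Extra trial olive oil goes to participants who share cooking, individuals are randomised, and no rule stops two co-residents from enrolling, so a usual-care participant could be exposed

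*Protocol*

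**What the plan says.** - **Supply (Protocol 6.2, Treatment Group).** The aim is broad: "We will aim to replace all free fats or fats added into meal preparation". For shared kitchens the protocol adds: "For participants with shared meal preparation responsibilities in the household, additional bottles of EVOO will be provided".
- **Allocation (Protocol 6.2).** "Participants within these two groups will be randomised after screening in a 1:1 ratio to nutrition intervention or usual care". The sequence is "stratified for presence/absence of disease and sex".
- **What the randomiser sees (Protocol 7.3).** "The investigator performing the randomisation will only be provided with Screening ID, age, and gender of the participant to perform the randomisation procedure". No household identifier is passed on.
- **Recruitment of healthy controls (Protocol 6.3).** "Recruitment will be achieved through community/social media advertising in the greater Sydney area alongside the recruitment strategy for participants with UC".
- **Eligibility (Protocol 6.3 and 7.1.1).** The nearest rule, UC exclusion 9 and healthy-control exclusion 11, is "Daily consumption of olive based product(s) in any form", judged from the diet history and medication list. No criterion mentions co-residents or shared meals.
- **Usual care (Protocol 6.2, Control Group).** "Participants will be asked to maintain their habitual lifestyle regarding diet and exercise throughout the study". Any changes are recorded.
- **Analysis (Protocol 6.5).** Intention to treat is primary, whatever the adherence.

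**The concern.** The protocol foresees that some intervention participants will cook with others and supplies oil for that situation. It does not consider that one of the others might be in the usual-care arm. Both disease groups are recruited in the same area over the same period, so a partner or housemate of a participant could volunteer. Nothing at screening or allocation would identify the pair.

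If the two fall in different arms, the usual-care member may eat food cooked in the study oil for up to four weeks and remain in the usual-care arm for analysis. That shrinks the between-arm difference in the Partial Mayo Score among UC participants, and in the gut bacterial profile in whichever disease group the exposed person belongs to. The arms are small, so a single case can matter. Eligibility and allocation are fixed in the protocol, and no later analysis plan can undo the exposure.

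**Working it through.** **1. Reproduce the plan's sample size (Protocol 6.4).** Inputs: a 2-point difference in the Partial Mayo Score, effect size 1.25, alpha 0.05, and 'beta 0.8' read as power 0.80. Two-sided testing is assumed because sidedness is not stated.
- Implied SD = 2 / 1.25 = 1.6.
- A two-sample t-test (noncentral t) gives power 79.6% at 11 per group and 83.3% at 12 per group. The stated 12 per group is reproduced.
- Dropout of 16%: 24 × 1.16 = 27.8, or 28; 24 / 0.84 = 28.6, or 29. The stated 28 is close enough for this purpose.

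**2. Chance that a co-resident pair is split.** A UC participant and a healthy co-resident are in different strata, so their 1:1 allocations are independent.
- P(different arms) = 2 × 0.5 × 0.5 = 0.50.
- P(UC member in usual care, healthy member on oil) = 0.5 × 0.5 = 0.25.
- P(healthy member in usual care, UC member on oil) = 0.25.

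**3. Pairs needed to produce one exposed UC control.** Expected number = 0.25 × number of UC/healthy pairs. One case therefore needs 1 / 0.25 = 4 pairs, two need 8 and three need 12. Twelve pairs would involve 12 of the 28 UC participants.

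**4. Effect on power, UC comparison.** Let k be the number of the 12 usual-care UC participants who receive the full effect of the oil. The diluted effect size is 1.25 × (1 − k/12). The last column lets the usual-care variance rise because that arm becomes a mixture: variance = 1.6² + (k/12)(1 − k/12) × 2², averaged with 1.6² from the other arm.

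| k (assumed) | Diluted effect size | Power, SD constant | Power, SD inflated |
|---|---|---|---|
| 0 | 1.25 | 83% | 83% |
| 1 | 1.15 | 76% | 74% |
| 2 | 1.04 | 68% | 64% |
| 3 | 0.94 | 59% | 54% |

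With 14 per group (all 28 recruited and no dropout), the constant-SD figures are 89%, 84%, 78% and 71%.

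**5. Which pairs the olive exclusion catches.** A housemate screened while already eating the trial oil daily would probably be excluded. Two people who enrol together, or one who is screened before the other's intervention starts, would not be.

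**The case against.** The strongest objection is that co-enrolment is hypothetical. No section plans or reports it, and recruiting healthy controls alongside UC participants describes an advertising channel, not an invitation to partners. That stands: the frequency is unknown and may be zero.

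There are also partial safeguards. The olive exclusion removes some later-enrolling housemates. Usual-care participants are asked to keep their diet, and weekly calls review lifestyle changes. Food records, plasma oleic acid and the olive-phenol markers in 9.1 could reveal exposure. These points stand too, but apart from the exclusion and the request to keep the usual diet they detect exposure rather than prevent it.

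Some stronger readings are tempting, and the document does not support them:

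- **The whole household is placed on the oil.** The text gives extra bottles where cooking is shared. The target quantity is calculated from the participant's own free-fat energy.
- **Half of co-enrolled pairs damage the UC comparison.** For UC/healthy pairs it is about a quarter. In another quarter the exposed person is a healthy control, who has no Partial Mayo outcome.
- **Returned bottles become an invalid adherence measure.** The protocol collects leftover bottles but never says that they measure intake. It lists other sources for that.
- **The exposed control loses a clean baseline.** Randomisation follows the baseline assessment, so exposure through the co-resident in weeks 1 to 4 comes after it.
- **The model wrongly lacks a household term.** That is detail commonly left to an analysis plan. With nearly all households contributing one person, it could hardly be estimated.

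**Conclusion.** The gap is real but minor. The protocol supplies extra oil for shared cooking, allocates individuals without sight of household, and has no rule against co-residents enrolling. Where a pair is split, the bias is towards no effect.

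The size depends on an unstated number of households. On the protocol's own inputs, one fully exposed UC control takes power from about 83% to about 76%, below the 80% target, at the planned evaluable size of 12 per group. If all 28 are recruited and none drops out, power with one such case is still about 84%. About four UC/healthy pairs would be expected to produce that one case, so the rows for two or three cases are unlikely for the disease-activity outcome. The illustration assumes two-sided testing and that the exposed control receives the full effect; partial exposure would dilute less. No power figure can be given for the healthy group, because 6.4 says its size does not rest on a hypothesis.

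**What to change.** Add one line to the exclusion lists for both groups in 6.3 and 7.1.1: *shares a household or regularly shares meals with a person already enrolled in the study*. Ask about it at the telephone screen. Confirm it just before randomisation, because under 7.1 people are enrolled only at that step and two co-residents could be in screening at once.

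Placing the second member in the first member's arm is not a good alternative. That allocation would be known before enrolment, which defeats the concealed scheme in 6.2.

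The cost is one eligibility line, one screening question and the loss of a few volunteers.
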